6.1.4.1 Elevation of Creatine Kinase (CK)

If CK is > 5x ULN, CK must be retested before IP is administered. In addition, investigators will ask study subjects to promptly report muscle pain, soreness, cramps, or weakness especially if accompanied by malaise or fever. If such symptoms occur and no scheduled study laboratory assessments are performed, the subject's CK levels should be measured by unscheduled assessment. If CK is > 5x ULN, the subject must be instructed as soon as possible to discontinue statin, other applicable lipid background therapy, and/or Amgen IP (evolocumab). CK must be retested before statin, other lipid background therapy, and/or IP (evolocumab) administration can be continued. A sample for urinalysis must be collected and sent to the central laboratory if CK is elevated > 10x ULN on retest as per table below.

The following rules apply for scheduled laboratory assessments and for unscheduled CK measurements:

CK at scheduled or unscheduled visit	CK on retest	Investigational Product and/or Statin and/or other lipid lowering therapies Administration
> 5x ULN	> 10x ULN	Discontinue both statin, other lipid lowering therapies, and IP ^a . Collect urine sample for urinalysis. Contact Amgen Medical Monitor.
	> 5x to ≤ 10x ULN	Discontinue statin, other lipid lowering therapies, and retest CK before administration. Consider continuing IP if alternative explanation.
	≤ 5x ULN	Consider continuing statin, other lipid lowering therapies and IP

^a CK elevations >10x ULN that have been confirmed to be secondary to myocardial infarction do not require discontinuation of statin, other lipid lowering therapy or IP

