6.1.4 Criteria for Withholding of Investigational Product

Reports from the central laboratory after each clinic visit must be reviewed as soon as possible after receipt and before the next administration of IP (evolocumab). If any of the criteria below are met for withholding IP, statin, or other applicable background lipid therapy, the subject must be instructed to stop the applicable treatment and an additional visit must be scheduled for the required laboratory evaluations. If a subject is experiencing elevations of laboratory values and is receiving other lipid therapies that may result in such elevations, eg, ezetimibe or niacin, the additional therapies should also be evaluated for a potential role in these elevations and considered for discontinuation. Ezetimibe or niacin can result in elevation of CK or liver function tests.

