- Clinical signs or symptoms that are, in the opinion of the investigator, consistent with hepatitis (such as right upper quadrant pain/tenderness, fever, nausea, vomiting, jaundice, rash or eosinophilia > 5%). If such signs or symptoms are coupled with ALT or AST elevations > 3x ULN, IP should be withheld.

If IP, statin and other applicable lipid background therapy is withheld due to any of the conditions above, the subject should be followed according to recommendations in [Appendix A](#) for possible DILI.

6.1.4.3 Criteria for Rechallenge After Withholding or Discontinuation of IP (Evolocumab), Statin and Other Applicable Lipid Background Therapy

The decision to re-challenge the subject after therapy changes due to CK elevation or elevation of liver function tests should be discussed and agreed upon unanimously by the subject, Principal Investigator, and Amgen.

If signs or symptoms recur with rechallenge of IP, then IP should be permanently discontinued. If signs or symptoms recur with rechallenge of statin background therapy, the statin may be substituted by another statin in consultation with the Amgen medical monitor, if possible, or the statin therapy may be discontinued. If signs or symptoms recur with rechallenge of other applicable lipid background therapy, this therapy may be discontinued.

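### The MI exemption in Protocol 6.1.4.1 stops at CK > 10x ULN, so a confirmed MI with a retest CK of > 5x to ≤ 10x ULN still triggers a hold of statin and other lipid therapy

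*Protocol*

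**What the plan says.** Protocol 6.1.4.1 works in two steps.

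**First CK above 5x ULN.** The narrative says "If CK is > 5x ULN, the subject must be instructed as soon as possible to discontinue statin", with other background lipid therapy "and/or" IP named in the same sentence, and then "CK must be retested before statin, other lipid background therapy, and/or IP (evolocumab) administration can be continued". Section 6.1.4 adds that "the subject must be instructed to stop the applicable treatment and an additional visit must be scheduled for the required laboratory evaluations".

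**Retest.** The table then sorts subjects by the retest value:

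- Above 10x ULN: "Discontinue both statin, other lipid lowering therapies, and IP". This row alone carries footnote a, which reads "CK elevations >10x ULN that have been confirmed to be secondary to myocardial infarction do not require discontinuation of statin", other lipid-lowering therapy or IP.
- Above 5x and up to 10x ULN: "Discontinue statin, other lipid lowering therapies, and retest CK before administration. Consider continuing IP if alternative explanation". There is no footnote.
- At or below 5x ULN: continuing all therapies may be considered.

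Section 6.1.4.3 covers resumption: "The decision to re-challenge the subject after therapy changes due to CK elevation or elevation of liver function tests should be discussed" and agreed unanimously by subject, investigator and sponsor. It has no MI exception.

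**The concern.** The sponsor has already decided that a CK rise caused by MI is no reason to stop lipid therapy, even above 10x ULN. Nothing in either document explains why that reasoning should fail between 5x and 10x. The middle row accepts that another cause matters, but only for IP.

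Every subject has known coronary disease, and Protocol 6.1.3 asks for optimized lipid lowering during the extension. A site that follows the middle row literally would hold statin and other lipid therapy just after a confirmed MI, when the same protocol calls that unnecessary at a higher CK from the same cause. What is at stake is a small matter of patient safety and of sites acting alike.

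**Working it through.** The plan gives no figure to reproduce here. The check is a reading of the rule by band, followed by a rough count of subjects.

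**Rule for a CK elevation confirmed as secondary to MI**

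| Retest CK | Statin and other lipid therapy | IP |
|---|---|---|
| > 10x ULN | Stop not required (footnote a) | Stop not required (footnote a) |
| > 5x to ≤ 10x ULN | Stop, retest before administration | May continue if alternative explanation |
| ≤ 5x ULN | Consider continuing | Consider continuing |

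The statin and lipid-therapy column is not monotone: strictest in the middle. No other MI exemption for the middle band appears in Protocol 6.1.4, 6.1.4.1 or 6.1.4.3. SAP 10.6.3 only tabulates CK above 5x and above 10x ULN.

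Footnote a does not say whether its threshold applies to the initial or the retest value. A subject first above 10x who falls into the middle band on retest is arguably covered. A subject at or below 10x on both tests clearly is not.

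**How many subjects**

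From the documents: 642 subjects, about 2 years, and 8 scheduled chemistry draws after Day 1 (Weeks 4, 12, 24, 36, 48, 52, 76, 104) in 104 x 7 = 728 days.

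Assumed, because the documents give no values: MI rate 1–3% per year; 10–30% of MIs in the middle band on retest; CK above 5x ULN for 2–7 days after MI; 3 days between first draw and retest.

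1. MIs: 642 x 2 x 0.01 = 12.84, to 642 x 2 x 0.03 = 38.52.
2. Middle band: 12.84 x 0.10 = 1.284, to 38.52 x 0.30 = 11.556.
3. The row needs two values above 5x ULN, so the usable window is the duration less the lag: 2 − 3, floored at 0, to 7 − 3 = 4 days.
4. Chance that a scheduled draw falls in the window: 8 x 0/728 = 0, to 8 x 4/728 = 4.4%.
5. Subjects: 1.284 x 0 = 0, to 11.556 x 0.04396 = 0.51.

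Sensitivity to the lag:

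| Lag (days) | Window (days) | Chance of a draw | Subjects |
|---|---|---|---|
| 1 | 1–6 | 1.1–6.6% | 0.01–0.76 |
| 2 | 0–5 | 0–5.5% | 0–0.63 |
| 3 | 0–4 | 0–4.4% | 0–0.51 |
| 5 | 0–2 | 0–2.2% | 0–0.25 |

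These counts ignore dropout and include subjects first above 10x whom footnote a may already cover, so on scheduled draws they lean high. They would be too low only if unscheduled CK values after an MI were acted on under the table. The table does apply to unscheduled measurements, but the stated trigger for "CK levels should be measured by unscheduled assessment" is muscle symptoms, and Protocol 7.2.2.5 sends on-study samples to the central laboratory. How often post-MI values would enter by this route is not stated.

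**The case against.** The strongest reply is that the difference between the bands is slight. The stop and retest after a first CK above 5x apply to both. Footnote a waives discontinuation but is silent on the retest condition, so even the higher band may wait for the first retest. What remains is the interval between the first retest and the next one. The middle row reads as a hold that loops back to a retest, whereas the > 10x row has no such step, so the exemption may have been placed where the stop is open-ended. All of this stands, and it limits the point to a short hold. It does not remove the hold, and the documents do not give this as the reason.

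Discretion is the second reply. The narrative and the table header both use and/or. Protocol 6.5 lets investigators change background therapy after Week 12 in line with local practice (92 of 104 weeks, 88%), and before that for compelling clinical reasons after contacting the medical monitor. This makes a rigid stop less likely. Neither provision rewords the row, which names statin and other lipid therapies outright.

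A reader might infer more than the text supports:

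- *That IP is also treated more strictly in the lower band.* The middle row's alternative-explanation relief covers IP, so no inversion for IP is shown.
- *That statin is stopped for good.* The row ties the stop to a further retest.
- *That only the lower band needs unanimous agreement to resume.* Section 6.1.4.3 may apply in both bands.
- *That Week 52 LDL-C or the event summaries are distorted.* Nothing in the documents points to this, and the expected count is too small.

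**Conclusion.** The inconsistency is real and minor. As written, an MI-related CK of > 5x to ≤ 10x ULN on retest triggers a hold of statin and other lipid therapy that footnote a would not require above 10x. That reading rests on the text alone and is firm where both CK values are ≤ 10x ULN; where the first value was above 10x, it depends on how footnote a is read.

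The size rests on assumption: fewer than one subject through scheduled draws at every lag tried, with an unknown addition from unscheduled values. The study is descriptive, and none of its planned summaries is affected.

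**What to change.** Mark the > 5x to ≤ 10x ULN row with a new footnote b, for example: *If MI is confirmed as the cause of the CK elevation (initial or retest value), statin and other lipid lowering therapies need not be stopped and need not await a further CK retest; IP is handled as stated in this row.*

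Add to the narrative's > 5x ULN stop and retest instructions an exception for statin and other background lipid therapy once MI is confirmed as the cause, pointing to footnotes a and b.

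Both parts are needed. Waiving the stop alone would leave the row's retest-before-administration condition holding up statin dosing. Confining the narrative exception to background therapy keeps the narrative and the row from diverging on IP. Leave the IP rules in the narrative, the table rows and footnote a unchanged.

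The cost is one footnote and one clause, in the next amendment or a clarification memo to sites. No new data or procedures are needed, and the stop remains for any CK elevation not confirmed as due to MI.

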6.1.4.2 Elevation of Liver Function Tests

Subjects with abnormal hepatic laboratory values (eg, alkaline phosphatase [ALP], AST, ALT, total bilirubin [TBL], or international normalized ratio [INR] or signs/symptoms of hepatitis may meet the criteria for withholding of IP, statin, and other applicable lipid background therapy. If the subject experiences an ALT or AST > 3X ULN, then they must be followed as detailed under section on close observation in [Appendix A](#).

IP, statin and other applicable lipid background therapy must be discontinued and the subject should be followed according to the recommendations in [Appendix A](#) (Additional Safety Assessment Information) for possible drug-induced liver injury (DILI), if ALL of the criteria below are met:

- TBL > 2x upper limit of normal (ULN) or INR > 1.5

AND

- AST or ALT > 3x ULN

AND

- no other cause for the combination of laboratory abnormalities is immediately apparent; important potential causes for abnormal AST/ALT or TBL values include, but are not limited to:
 - Obstructive gall bladder or bile duct disease
 - Viral or alcoholic hepatitis (eg, Hepatitis A/B/C/D/E, Epstein-Barr Virus, cytomegalovirus, Herpes Simplex Virus, Varicella, etc)
 - Progression of malignancy involving the liver (note that metastatic disease to the liver, by itself, should not be used as an explanation for significant AST/ALT elevations)
 - Hypoxic or ischemic hepatopathy or congestive hepatopathy in association with significant right sided heart failure
 - Concomitant administration of other hepatotoxins, including drugs that inhibit bilirubin glucuronidation (eg, indinavir, atazanavir, irinotecan) or herbal or dietary supplements
 - Heritable disorders causing impaired glucuronidation (eg, Gilbert's Syndrome); alpha-one antitrypsin deficiency
 - Autoimmune hepatitis
 - Nonalcoholic steatohepatitis (NASH) or other fatty liver disease

IP, statin and other applicable lipid background therapy should also be withheld and the subject should be evaluated for DILI if ANY of the following criteria are met:

- AST or ALT > 8x ULN at any time
- AST or ALT > 5x ULN but < 8x ULN for ≥ 2 weeks
- TBL > 3x ULN at any time

- ALP > 8x ULN at any time
- Clinical signs or symptoms that are, in the opinion of the investigator, consistent with hepatitis (such as right upper quadrant pain/tenderness, fever, nausea, vomiting, jaundice, rash or eosinophilia > 5%). If such signs or symptoms are coupled with ALT or AST elevations > 3x ULN, IP should be withheld.

If IP, statin and other applicable lipid background therapy is withheld due to any of the conditions above, the subject should be followed according to recommendations in [Appendix A](#) for possible DILI.

6.1.4.3 Criteria for Rechallenge After Withholding or Discontinuation of IP (Evolocumab), Statin and Other Applicable Lipid Background Therapy

The decision to re-challenge the subject after therapy changes due to CK elevation or elevation of liver function tests should be discussed and agreed upon unanimously by the subject, Principal Investigator, and Amgen.

If signs or symptoms recur with rechallenge of IP, then IP should be permanently discontinued. If signs or symptoms recur with rechallenge of statin background therapy, the statin may be substituted by another statin in consultation with the Amgen medical monitor, if possible, or the statin therapy may be discontinued. If signs or symptoms recur with rechallenge of other applicable lipid background therapy, this therapy may be discontinued.

6.2 Background Atorvastatin Lipid-Lowering Therapy

Atorvastatin will be provided for the first 12 weeks of this study for subjects who were taking Amgen-supplied atorvastatin in the parent study GLAGOV and continue into this extension study.

All other lipid-regulating drugs that are allowed per protocol and prescribed for the subject, must be commercially available and are not provided or reimbursed by Amgen (except if required by local regulation). The investigator will be responsible for obtaining supplies of these drugs.

6.3 Medical Devices

IP will be administered per via three prefilled AI/Pens or one 3.5 AMD, provided by Amgen ([Section 6.1](#)). Additional details regarding the use of the AI/Pens and the 3.5 mL AMD are provided in the IPIM and in the Instructions for Use (IFU) brochure.

Medical supplies (eg, alcohol prep pads), that are commercially available are not usually provided or reimbursed by Amgen (except, for example, if required by local regulation). The Investigator will be responsible for obtaining these necessary medical supplies.

6.4 Product Complaints, Including Device Complaints

A product complaint is defined as any written, electronic or oral communication that alleges deficiencies related to the identity, quality, durability, reliability, safety, effectiveness, or performance of a drug or device after it is released for distribution to market or clinic by either Amgen or by distributors and partners for whom Amgen manufactures the material.

Any product complaints associated with an investigational product(s) or non-investigational product(s) or device(s) supplied by Amgen are to be reported according to the instructions provided in the IPIM.

Concerns or irregularities about the packaging, appearance or usage of the prefilled AI/Pen or AMD or other Amgen provided, protocol-required product in this study are to be reported to Amgen within 24 hours of discovery or notification of the concern or irregularity. Should any such concerns or irregularities occur please do not use the IP until Amgen confirms that it is permissible to use.

Examples of potential product complaints that need to be reported to Amgen include, but are not limited to:

- broken container or cracked container
- usage of the AI/pen due to misunderstanding of the IFU or error on the part of the user, or other inability to appropriately use the product
- devices: issues with delivery of IP by device or malfunction of the AI/pen or 3.5 mL AMD (eg, bent or broken needle, cracked or broken barrel, etc.)
- missing labels, illegible labels, incorrect labels, and/or suspect labels
- change in IP appearance, for example color change or visible presence of foreign material
- unexpected quantity or volume, for example number of tablets or amount of fluid in the prefilled AI/Pen or 3.5 mL AMD cartridge
- evidence of tampering or stolen material

If possible, please have the AI/Pen or 3.5 mL AMD cartridge or other Amgen provided protocol-required suspect product available for examination when making a product complaint. Maintain AI/Pen or 3.5 mL AMD cartridge or other Amgen provided protocol-required suspect product at appropriate storage conditions until further instructions are received from Amgen.

The investigator is responsible for ensuring that all product complaints observed by the investigator or reported by the subject that occur after signing of the informed consent through 30 days after the last dose of IP or EOS, whichever is later, are reported to Amgen within 24 hours of discovery or notification of the product complaint.

For more details regarding the identification and reporting of product and device complaints, refer to the IPIM and the IFU.

6.5 Concomitant Therapy, Physical Exercise, and Diet

Prior to week 12 lipid-regulating concomitant lipid-regulating medications cannot be altered (since lipid testing is prohibited), unless there is a clinically compelling reason for change. The investigator must contact the Amgen medical monitor to discuss such cases on an individual basis. After the masked period (Week 12 visit), laboratory results ([Section 7.2.2.4](#)) will no longer be masked and investigators may alter background lipid-regulating therapy per local standards of care. All subjects should maintain their current regimen of diet and exercise for at least the first 12 weeks of the study, but should also be encouraged to continue to do so through the remainder of the study. Subjects will be required to refrain from unaccustomed intensive exercise (eg, heavy lifting, long runs or other strenuous activity) 48 hours prior to each visit since such activity could affect creatine kinase levels.

6.6 Excluded Treatments During Study Period

The use of magnesium or aluminum hydroxide-containing antacids is not recommended within the period of two hours before and two hours after dosing with statins given the potential for interference with absorption.

7. STUDY PROCEDURES

Subjects that successfully complete study 20120153 and completed IP (evolocumab) in study 20120153 will be eligible to enroll in this study. In addition, subjects will need to meet eligibility criteria. Subjects will need to sign a new study informed consent form. Subject numbers will be the same as those in their parent study. Subjects will visit the site on Day 1 and week 4. Thereafter, subjects will visit the site quarterly for the first year and two additional times during year 2. During these visits vital signs will be obtained and adverse events (AEs), serious adverse events (SAEs), concomitant medications will be recorded, and central laboratory tests will be performed. All subjects will receive open-label evolocumab for approximately 2 years (or until the investigator's recommendation of discontinuation, Amgen's recommendation of discontinuation, the subject's decision to discontinue for any reason, or until an administrative decision is

made to close the study). For the purpose of this study, a month is defined as 4 weeks and a quarter is defined as 12 weeks.

Written informed consent must be obtained and will be implemented before protocol specific procedures are carried out. The risks and benefits of participating in the study will be verbally explained to each potential subject prior to entering into the study. The procedures to be performed at each clinic visit are described below. IP should not be administered until all study procedures are completed at each visit. Subject visit schedule will be the same for all subjects. **In addition to the protocol-specified study procedures and assessments described below, investigators should continue to routinely monitor subjects according to local disease management guidelines and perform assessments (eg. ECG, hemoglobin A1c, eGFR, and hematology), as applicable, in routine care.**

7.1 Schedule of Assessments

Study Day / Timepoint	YEAR 1				YEAR 2	
	EOS Parent Day 1 OLE ^a	Week 4	Quarterly Visits Weeks: 12, 24, 36, and 48	Week 52	Month 6 (Week 76)	Year 2 (Wk 104) EOS/ET OLE ^e
General Procedures						
Medical History	X					
Informed consent	X					
Vital Signs (HR, BP)	X	X	X	X	X	X
AEs/SAEs/CV Events	X	X	X	X	X	X
Concomitant medication	X	X	X	X	X	X
Body Weight	X			X		X
Waist circumference	X			X		X
Physical exam	X			X		X
Central Laboratory						
Fasting Lipids	X	X	X	X	X	X
Chemistry	X	X	X	X	X	X
Serum pregnancy (females of childbearing potential) and FSH	X ^b	X ^c	X ^c	X ^c	X ^c	X
Investigational Product						
IP dispense ^d	X	X	X	X	X	
IP reconcile	X	X	X	X	X	X

^a D1 = day of first administration of investigational product for the open-label extension (OLE); subjects will sign a new OLE consent.

^b FSH = in applicable subjects for study entry only – see [exclusion criteria](#)

^c Serum pregnancy testing will occur at week 4, week 24, week 52, and every 6 months thereafter.

^d Subjects or caregivers will administer evolocumab monthly both at site visits and between site visits. Last IP will be administered at week 100.

^e The EOS procedures should be used as a guide for the depth of information obtained for any subject that elects to discontinue IP but continue via follow-up (see [section 8](#)).

7.2 General Study Procedures

7.2.1 Enrollment (Week 80 Parent/Day 1 OLE + 14 days)

Day 1 for OLE study and the week 80 visit for the parent study should occur on the same day. All efforts should be made to minimize any time gaps between the parent study EOS and Day 1 in the OLE study. The following procedures will be performed:

- Obtain consent
- Medical History
- Vital signs: sitting blood pressure (BP), heart rate (HR)

- AEs/SAEs/CV Events
- Concomitant medications
- Body weight and waist circumference
- Physical exam
- Blood draw for serum pregnancy (females of childbearing potential only) and FSH (for applicable subjects)
- Blood draw for fasting lipids (≥ 9 hour fasting sample) and chemistry
- Dispense and reconcile IP
- Observe IP Administration evolocumab (AMG 145) QM unless subject elects not to self-inject (must be after completion of vital signs, and blood draw procedures).

Enrollment - subjects will have the risks and benefits of participating in this study explained to them. Subjects that meet inclusion/exclusion criteria will need to sign a new OLE informed consent form, if they already have not done so, before enrolling. Subjects will administered their first injection at the site (must be after completion of vital signs and blood draw procedures). Self-administration, defined as SC administration of IP by the subject or designee, will occur between visits to the investigator site (eg, at home). The patient (or designee) must have demonstrated competency at administration of SC injections before self-administration is permitted: the first two self-administered doses must be administered in a clinic by the patient or designee under the supervision of a healthcare provider. Day 1 is defined as the first day that protocol-specified investigational product is administered.

The following visits are for Year 1 only:

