4.2 Exclusion Criteria

Subjects will be **ineligible** for the study if they fulfill any of the following criteria:

1. Female subject of reproductive potential not willing to inform her sexual partner of her participation in the clinical study and to use an acceptable method(s) of **effective** birth control during treatment with evolocumab and for an additional 15 weeks after the end of treatment with evolocumab. Female subjects who have had a hysterectomy, bilateral salpingectomy, bilateral oophorectomy, or who are postmenopausal are not required to use contraception.
 - Postmenopausal is defined as: Age \geq 55 years with cessation of menses for 12 months or more; Age < 55 by no spontaneous menses for at least 2 years; Age < 55 years and no spontaneous menses within the past 1 year, but currently amenorrheic AND with postmenopausal gonadotropin levels (luteinizing hormone and follicle-stimulating hormone levels > 40 IU/L) or postmenopausal estradiol levels (< 5 ng/dL) or according to the definition of "postmenopausal range" for the laboratory involved.
 - Acceptable methods of **effective birth control include: sexual abstinence (when this is in line with the preferred and usual lifestyle of the subject. [Periodic abstinence (eg., calendar, ovulation, symptothermal, post-ovulation methods), declaration of abstinence for the duration of a trial, and withdrawal are not acceptable methods of contraception])**, surgical contraceptive methods (vasectomy or bilateral tubal ligation), use of hormonal birth control methods (pills, shots, implants or patches), intrauterine devices (IUDs), or two (2) barrier methods (each partner must use one barrier method) with spermicide – males must use a condom with spermicide; females must choose either a Diaphragm with spermicide, OR Cervical cap with spermicide, OR Contraceptive sponge with spermicide.

- *Note: Additional medications given during treatment with evolocumab may alter the contraceptive requirements. These additional medications may require an increase in the number of contraceptive methods and/or length of time that contraception is to be utilized after the last dose of protocol-required therapies. The investigator is to discuss these contraceptive changes with the study subject.*
2. Subject is pregnant or breast feeding, or planning to become pregnant or planning to breastfeed during treatment with evolocumab and within 15 weeks after the end of treatment with evolocumab

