6.1.1 Dosage, Administration, and Schedule

IP will be administered at the investigator site during scheduled visits via self-administration or by a qualified staff member. Between scheduled visits to the site, IP will be administered at home or other locations by subjects (or designee, which may include a qualified health care professional) in accordance with instructions in the IPIM.

Subjects who prefer not to self-administer IP may return to the study site for administration by qualified site personnel.

IP administration at each on-site visit must be done after vital signs, ECG, and blood draw procedures, if applicable. The date, time, and volume of evolocumab administered will be collected and recorded on the individual subject's electronic Case Report Form (eCRF) for doses administered at the study site. During the first two IP administrations

(day 1 and week 4), subjects will be kept for observation for at least 30 minutes before being discharged.

Self-administration, defined as SC administration of IP by the subject or designee, will occur on a monthly basis between visits to the investigator site (eg, at home). The patient (or designee) must have demonstrated competency at administration of SC injections before self-administration is permitted: the first two self-administered doses must be administered in a clinic by the patient or designee under the supervision of a healthcare provider.

IP will be administered with a total volume of 3.0 mL QM, via 3 separate autoinjections or with a total volume of 3.5 mL QM via 1 administration by a AMD. Injection sites should be rotated throughout the study. The autoinjector SC injections should be administered in a consecutive fashion with all injections completed within 30 minutes.

Details of preparing and administering all study products are included in the IPIM provided by Amgen prior to the start of the study.

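### The first extension dose waits for the Day 1 pregnancy sample to be drawn, but no section requires a negative result before dosing

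*Protocol*

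**What the plan says.** **Eligibility.** Protocol 4.2, exclusion 2, begins: "Subject is pregnant or breast feeding, or planning to become pregnant". Exclusion 1, on contraception, begins: "Female subject of reproductive potential not willing to inform her sexual partner of her participation in the clinical study". Neither says which test or result is needed, or by when. Section 7 adds: "In addition, subjects will need to meet eligibility criteria".

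**The entry test.** Section 7.2.1 lists serum pregnancy on Day 1 as a blood draw. The Schedule (7.1) places it under the central laboratory, and 7.2.2.5 sends all samples there. Neither the Schedule nor Table 1 contains a urine test, a local test or an earlier screening test. Footnote b, attached to the Day 1 entry, deals with FSH only.

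**Day 1.** Footnote a of the Schedule reads: "D1 = day of first administration of investigational product for the open-label extension (OLE". Section 7.2.1 asks that Day 1 fall on the same day as the parent week 80 visit and that any gap be kept small. Its heading allows up to 14 days more.

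**Order of events.** For the first dose, 7.2.1 says: "Subjects will administered their first injection at the site (must be after completion of vital signs and blood draw procedures". For on-site doses in general, 6.1.1 says: "IP administration at each on-site visit must be done after vital signs, ECG, and blood draw procedures, if applicable". Section 7 says: "IP should not be administered until all study procedures are completed at each visit".

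**Review of results.** Under 6.1.4, central laboratory reports "must be reviewed as soon as possible after receipt and before the next administration of IP (evolocumab").

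**The concern.** The Day 1 serum test is the extension's only scheduled means of finding an unrecognised pregnancy at entry. A result that arrives after the dose cannot do that for the dose already given. The contraception and planned-pregnancy exclusions lower the chance of pregnancy but do not detect one.

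The protocol itself treats exposure in pregnancy as important. It asks for contraception until 15 weeks after treatment ends (4.2) and for pregnancy monitoring over the same period (9.3), and it lists pregnancy as a reason to stop the investigational product (8.1). For a woman who received placebo in the parent study, the Day 1 injection would be her first evolocumab dose, and it cannot be withdrawn once given. What is at stake is subject safety, not the analysis.

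**Working it through.** The plan states no figure to reproduce. The check asks what each rule makes the first dose wait for.

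1. **Section 7.2.1 (specific to Day 1).** The dose must follow vital signs and the blood draw. No result is named.
2. **Section 6.1.1 (all on-site doses).** The condition is the same, with ECG where applicable. No result is named.
3. **Section 7 (general).** The dose must follow all study procedures. This could be read to include obtaining the result, but the procedure that 7.2.1 lists is the draw.
4. **Section 5 (enrollment).** A subject counts as enrolled after the parent end-of-study visit and signed consent. No laboratory result is needed.
5. **Section 6.1.4 (laboratory review).** Reports are reviewed after receipt and before the following dose. This protects the week 4 dose, not the Day 1 dose.
6. **Section 4.2 with section 7 (eligibility).** A known pregnancy disqualifies. The evidence needed, and its date, are not specified.

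No rule requires a negative result before the first dose. The same-day and small-gap instructions in 7.2.1 push a site towards dosing at that visit.

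**Doses possible before review is required.**

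- Inputs: 420 mg every 4 weeks with a window of ± 7 days (Synopsis, Glossary), and the next visit at week 4 ± 7 days (7.2.1.1).
- Time from first to second dose: 28 − 7 = 21 days to 28 + 7 = 35 days.
- With the report received in that interval and reviewed as 6.1.4 requires, the doses given with status unconfirmed number 1, or 1 × 420 mg = 420 mg.

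**Two conditions the documents do not settle.** The gap opens only if there is no recent parent-study pregnancy result and the central laboratory does not report on the day of the draw. The extension protocol gives no turnaround time and does not refer to a parent-study result.

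**Effect on the analysis.** The full analysis set is all enrolled subjects (Protocol 10.1.5, SAP 7.1), and enrollment does not depend on the test. If a dose is held, samples drawn earlier still fall in the Week 0 window, which accepts any study day up to 1 (SAP Appendix A).

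**The case against.** The strongest reply is that 7.2.1 and 6.1.1 are rules of sequence. They say what must come before the injection, not that a completed draw is enough to allow it. Permission comes from eligibility, and a pregnant woman is ineligible. Section 7 can be read to include the result, and the +14-day window lets a site wait without a deviation.

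Much of this stands. A reader might infer that the protocol permits dosing a pregnant woman. It does not: exclusion 2 still binds, and a known pregnancy bars the dose. The gap is narrower. The protocol does not require pregnancy status to be confirmed before the first dose, so a site that follows the same-day instruction can dose without knowing.

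A second reply is that the parent protocol and the laboratory manual are not available, so a recent result may exist or turnaround may be fast. That also stands and is why the point is conditional. But nothing in the extension protocol tells a site to obtain or use such a result.

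A third reply is that the design relies on contraception more than testing. Tests fall at weeks 4, 24 and 52 and then six-monthly. A woman who conceives just after the week 24 test could receive the doses at weeks 28, 32, 36, 40, 44 and 48, six in all, before the next scheduled test. That is fair, and it keeps the Day 1 point small. It does not explain why a test placed at entry should not inform entry.

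**Conclusion.** The point holds as a conditional safety gap that is cheap to close. If no recent parent-study result exists and the Day 1 result does not return the same day, the written rules let a woman of childbearing potential receive one 420 mg dose with her pregnancy status unconfirmed. The one-dose limit assumes that the report arrives before week 4 and is reviewed as 6.1.4 requires.

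The number of pregnant women affected is probably near zero and cannot be estimated from the documents. A reader might be tempted to multiply assumed rates. If 1% to 5% of the 642 expected subjects were women of childbearing potential, that would be 642 × 0.01 = 6.4 to 642 × 0.05 = 32.1 women. If 0.1% to 1% of those were unknowingly pregnant, it would be 6.42 × 0.001 = 0.006 to 32.1 × 0.01 = 0.32 women. Both rates are assumptions, because the documents give no split by sex or age. The count also takes in all 642 subjects, including those already treated with evolocumab in the parent study. It should not be quoted as the size of the problem.

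A reader might also infer that every such woman faces a first exposure. That applies only to former-placebo women. No endpoint, analysis or sample size changes.

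**What to change.** Keep the Day 1 serum sample. Add to Protocol 7.2.1 and to footnote b of the Schedule:

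*For females of childbearing potential, a negative pregnancy result must be available before the first OLE IP administration; use a parent-study result from shortly before Day 1 if one exists, otherwise give the first dose once the Day 1 result returns, within the +14-day window.*

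The entry sample should not be moved earlier to meet this, because an older sample can miss a pregnancy that the current one would detect. The +14 days is a visit window for starting the extension and says nothing about how long a pregnancy result stays valid. The sponsor should set separately how recent a parent-study result must be.

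The cost is one sentence in two places and no additional test. A few women may need a short dose hold or a separate dosing visit. That works against the instruction in 7.2.1 to minimize the gap after the parent study, but only for women of childbearing potential who have no recent negative result.
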